#### 9.14.4 Intra and Inter-reader Variability

## 9.14.4.1 Intra-reader Variability

Sample size calculations were performed to determine the number of Day 0 and Day 1 scans to be re-read by the central readers to assess for intra-reader variability. The proportion of positive/negative Cu-SAR-bisPSMA PET/CT scans for PC was assumed to be the same as for

September 4, 2024 CONFIDENTIAL Page 34 of 46

results seen in a similar study of F-DCFPyL-PCT/CT (the CONDOR study: https://www.ncbi.nlm.nih.gov/pmc/articles/PMC8382991/), where 62% were positive, 38% negative, with a Kappa of 0.917 for the intra-reader variability. Using a Kappa for the null hypothesis of 0.3, a sample size of 16 re-reads provides 91% power for the intra-reader variability analysis for each timepoint (16 re-reads at Day 0 and 16 at Day 1).

A random subset of 16 participants' Day 0 or Day 1 Cu-SAR-bisPSMA PET/CT scans will be evaluated twice by each of the central readers in order to assess the reproducibility of the readings and consistency among the readers. A total of 16 Day 0 and 16 Day 1 scans will be re-evaluated (they may not be the same participants as each timepoint will be randomized separately). The results from the second evaluation will only be used for intra-reader variability assessment and in no other analyses.

For each scan evaluated twice, both the original and 2nd evaluation results will be summarized for each region and participant-level for Cu-SAR-bisPSMA PET/CT positivity and total number of positive lesions. The intra-reader variability will be assessed for each reader separately using Cohen's pairwise kappa statistics along with 95% CIs for the dichotomous results (PET-positive or not), and the percent agreement (Lin's concordance correlation coefficient), along with 95% CI, for the continuous result (average number of positive lesions) for all participants that have two scan interpretations on a participant-level and region-level. The interpretations of Cohen's kappa are presented in Table 4.

Table 4 Cohen's Kappa Levels of Agreement

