10.4.6 Intra- and Inter-reader Reliability Assessments

A subset of each central reader's ⁶⁴Cu-SAR-bisPSMA PET/CT scans will be evaluated twice to assess the reproducibility of the readings and consistency among readers.

The intra-reader variability of each reader will be assessed by calculating percent agreement (concordance) and Cohen's pairwise kappa statistics along with the 95% CIs for the dichotomous results for all participants with two scan interpretations.

For inter-reader variability, the agreement among the three independent readers will be assessed by calculating percent pairwise concordance and Fleiss's overall multi-assessor kappa statistics and its 95% CIs.

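### SAP 9.14.4.1 omits the percent agreement that the protocol specifies for the intra-reader positive/negative read, and puts that label on Lin's coefficient for lesion counts

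*SAP*

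**What the plan says.** For intra-reader variability, Protocol 10.4.6 plans "calculating percent agreement (concordance) and Cohen's pairwise kappa statistics along with the 95% CIs for the dichotomous results". Both statistics therefore attach to the positive/negative read.

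SAP 9.14.4.1 divides them. The positive/negative read gets "Cohen's pairwise kappa statistics along with 95% CIs for the dichotomous results (PET-positive or not". The lesion count gets "the percent agreement (Lin's concordance correlation coefficient", with a 95% interval. Both are to be given at participant level and region level. The section also says that the original and second evaluations will be summarized for positivity and lesion number, but it defines no agreement percentage from them.

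The number of re-reads rests on a similar study, "where 62% were positive, 38% negative, with a Kappa of 0.917 for the intra-reader variability". The SAP then states: "Using a Kappa for the null hypothesis of 0.3, a sample size of 16 re-reads provides 91% power". On volume it says: "A total of 16 Day 0 and 16 Day 1 scans will be re-evaluated".

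Two other places bear on this. SAP 9.14.4.2 keeps percent pairwise concordance, with a formula, for the positive/negative read between readers. SAP Table 3 (section 8.0), which lists deviations from the protocol analyses, has one entry, on lesion-to-background ratio.

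**The concern.** A statistic specified in the protocol disappears from the SAP without being listed as a change, and its name moves to something else. Lin's concordance correlation coefficient runs from -1 to 1 and measures how closely two sets of numerical values agree. A reader of the study report who sees a percent agreement of, say, 0.9 would take it to mean that 90% of repeat reads gave the same positive/negative result, which it does not. One possible cause is that the protocol's word concordance was read as the name of Lin's coefficient.

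The gap is more than one of labelling because the re-read sample is small. With 16 pairs and reproducible readers, perfect agreement is a likely outcome. Kappa and its usual interval then convey no uncertainty, whereas a simple proportion with an exact interval does.

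**Working it through.** **Inputs.** Proportion positive p = 0.62, kappa 0.917, null kappa 0.3 and n = 16 per reader and day are from SAP 9.14.4.1. Alpha 0.05 is from SAP 9.14; sidedness is not stated for this calculation. The figures of 65% of participants positive and 1.3 positive regions each are from SAP 4.2, and the five regions from SAP Table 2. Region prevalences of 5% and 2% are assumptions.

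**The SAP's own figure.** A large-sample test of one kappa, with equal margins 0.62/0.38, has variance terms 0.9536 under the null and 0.1692 under the alternative. With two-sided alpha 0.05:

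Power = Φ[(√16 × (0.917 − 0.3) − 1.96 × √0.9536) / √0.1692] = Φ(1.347) = 0.911.

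The stated 91% reproduces.

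**Perfect agreement at participant level.** The chance that one pair of reads disagrees is 2p(1 − p)(1 − kappa) = 2 × 0.62 × 0.38 × 0.083 = 0.0391, so expected agreement is 96.1%. The chance that all 16 pairs agree is 0.9609^16 = 0.528. Varying the true kappa at p = 0.62:

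| True kappa | Disagreement per pair | P(all 16 agree) |
|---|---|---|
| 0.70 | 0.1414 | 9% |
| 0.80 | 0.0942 | 21% |
| 0.90 | 0.0471 | 46% |
| 0.917 | 0.0391 | 53% |
| 0.95 | 0.0236 | 68% |

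Three readers and two days give six participant-level kappas. At 0.917, 6 × 0.528 = about 3 of them are expected to show perfect agreement. Kappa is then 1, the asymptotic standard error is zero and the interval is 1.00 to 1.00.

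**Undefined kappa.** This needs all 32 reads in one category. At participant level both reads are positive with probability 0.6004 and both negative with probability 0.3604, so the chance is 0.6004^16 + 0.3604^16 = 0.0003, or 0.03%.

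For a single region with prevalence q, both reads are negative with probability (1 − q)² + q(1 − q) × kappa. Mean prevalence from the planning figures is 0.65 × 1.3 / 5 = 0.169. At kappa 0.917:

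| Region prevalence | Both reads negative | P(undefined), 16 pairs |
|---|---|---|
| 0.169 (from SAP 4.2) | 0.8193 | 4% |
| 0.05 (assumed) | 0.9461 | 41% |
| 0.02 (assumed) | 0.9784 | 70% |

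**The missing statistic.** Clopper-Pearson 95% intervals for observed agreement:

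- 16/16: 100% (79.4% to 100%), where the lower limit is 0.025^(1/16) = 0.794
- 15/16: 93.8% (69.8% to 99.8%)
- 14/16: 87.5% (61.7% to 98.4%)

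These remain defined and informative where the kappa interval does not.

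**The case against.** A reader might infer that kappa fails in about half of cases. The documents do not support that. Almost all of the 53% at participant level is perfect agreement, where kappa = 1 is a correct estimate and only the interval is poor. The zero-width interval also depends on an asymptotic method, and the SAP names no method for the kappa interval. The 53% further depends on a kappa of 0.917 taken from another study.

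A reader might also infer that the plan is left with no usable measure of intra-reader reproducibility. That goes too far. SAP 9.14.4.1 summarizes both evaluations and gives Lin's coefficient for lesion counts, which can differ even when positivity agrees fully. SAP 9.14 says that region-level analyses are run on all regions together as well as singly unless otherwise specified. By that default there is a pooled kappa on 16 × 5 = 80 pairs per reader and day. At prevalence 0.169 the disagreement per pair is 2 × 0.169 × 0.831 × 0.083 = 0.0233. If pairs are treated as independent (an assumption), all 80 agree with probability (1 − 0.0233)^80 = 15%.

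The high chances of an undefined kappa come from assumed prevalences; the figure derived from the SAP is 4%. Finally, the endpoint is exploratory, SAP 4.1 plans no formal hypothesis testing, and no primary or secondary result depends on it.

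All of this stands and limits the size of the point. None of it answers the omission, the wrong label, or the absence from SAP Table 3.

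**Conclusion.** The point holds as a minor one. The omission and the mislabelling can be read directly from the two texts and do not depend on the true kappa. The retention of percent concordance in SAP 9.14.4.2, and the silence of SAP Table 3, suggest an oversight more than a decision.

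The practical consequence is conditional. Perfect agreement in all 16 pairs has a probability between 9% and 53% for a true kappa between 0.70 and 0.917 at 62% positive. Only then, and only with an asymptotic interval, does the plan print false certainty for the participant-level read. An undefined kappa is a matter for single regions that are rarely positive, and the SAP gives no rule for it. The stated 91% power is not affected.

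**What to change.** In SAP 9.14.4.1:

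1. For PET positivity, report the number of concordant pairs divided by the number re-read with evaluable results, with a Clopper-Pearson 95% interval, beside kappa. Do this by reader and day, at participant level and for each region. The percentage follows the approach of SAP 9.14.4.2. The interval is an addition to it, because that section states intervals for Fleiss's kappa but not for percent concordance.
2. Report kappa as not estimable when all reads fall in one category, and rely on the exact agreement interval when agreement is perfect.
3. Report Lin's coefficient under its own name, for lesion counts only.
4. If any departure from Protocol 10.4.6 is intended, list it in SAP Table 3 with a reason.

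The cost is a few table columns and some sentences. No new data or reads are needed.

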## Value of Kappa Level of Agreement % of Data that are Reliable

020	None	0–4%
.2139	Minimal	4–15%
.4059	Weak	15–35%
.60–.79	Moderate	35–63%
.8090	Strong	64-81%
Above .90	Almost Perfect	82–100%

The second evaluation of the scans by the central readers will include all of the same data points as the first, original evaluation. The following variables will be assessed for intra-reader variability:

- Participant and region-level Cu-SAR-bisPSMA PET/CT positivity described in the Primary Endpoint analysis
- Average number of positive lesions at participant and region-level

September 4, 2024 CONFIDENTIAL Page 35 of 46

## 9.14.4.2 Inter-reader Variability

For dichotomous results of Cu-SAR-bisPSMA PET/CT positivity, the agreement among the 3 independent readers will be assessed in pairs by calculating the percent pairwise concordance, defined as: (# of concordant values across the 2 readers) / (# of concordant values + # of discordant values across the 2 readers) with evaluable Cu-SAR-bisPSMA PET/CT data. Additionally, Fleiss's overall multi-assessor kappa statistics with 95% CIs will be presented for all 3 readers together for the same parameter. Day 0 and Day 1 Cu-SAR-bisPSMA PET/CT scans will be analyzed individually.

For the continuous measures related to the total number of positive lesions for participant-level and the 5 regions individually, Pearson interclass correlations (ICC) will be presented with 95% CIs. Additionally, Bland-Altman plots will be produced to assess the agreement visually for the 6 points. This will be done as reader 1 vs. reader 2, reader 1 vs. reader 3, and reader 2 vs. reader 3.

The following variables will be assessed for inter-reader variability:

- Participant and region-level Cu-SAR-bisPSMA PET/CT positivity
- Number of positive lesions at participant and region-level

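### Read literally, the inter-reader coefficient for lesion counts is a Pearson correlation, which measures linear association and not agreement (exploratory endpoint, minor)

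*SAP*

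**What the plan says.** SAP 9.14.4.2 treats positivity and lesion counts separately.

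- **Positivity (yes/no).** Percent concordance is given for each reader pair, and "Fleiss's overall multi-assessor kappa statistics with 95% CIs will be presented for all 3 readers together". Protocol 10.4.6 asks for this much and no more: "percent pairwise concordance and Fleiss's overall multi-assessor kappa statistics and its 95% CIs".
- **Lesion counts.** The scope is set by the words "For the continuous measures related to the total number of positive lesions for participant-level and the 5 regions individually". For these six measures the section names its statistic as follows: "Pearson interclass correlations (ICC) will be presented with 95% CIs". No formula and no intraclass model or form is given. The next sentences read "Additionally, Bland-Altman plots will be produced to assess the agreement visually for the 6 points" and "This will be done as reader 1 vs. reader 2, reader 1 vs. reader 3, and reader 2 vs. reader 3". No tabulated mean difference or limits of agreement are mentioned.

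For counts within a reader, SAP 9.14.4.1 uses "the percent agreement (Lin's concordance correlation coefficient), along with 95% CI, for the continuous result (average number of positive lesions").

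The objective in Protocol 2.7.3 and SAP 3.1.3 is reproducibility of the readings and consistency among readers. It is exploratory, and the inter-reader endpoint listed under it is kappa. The count coefficient is an addition made in the SAP.

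**The concern.** Both Pearson and interclass point to the ordinary product-moment correlation. That statistic asks whether two readers' counts lie on a straight line, not whether they are the same counts. A reader who reports twice as many lesions in every participant correlates perfectly with a colleague. The abbreviation ICC normally stands for the intraclass correlation, which is a different statistic, so the text does not settle what will be programmed.

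The choice also sits oddly beside 9.14.4.1. Lin's coefficient penalises shifts in location and scale, and the SAP uses it where systematic differences are least likely, namely within one reader. Between readers, where over-calling and under-calling are more plausible, it names a coefficient that ignores them. The two figures could appear together in the study report without being comparable.

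At stake is one reported measure of reader consistency, with a confidence interval, that can look better than the agreement it is meant to describe. Lesion counts by reader also feed SAP 9.14.3.4 and 9.14.3.5, so readers of the report will want a sound figure.

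**Working it through.** The plan gives no target value, power or sample size for inter-reader agreement on counts, so there is no figure to reproduce. The check is how the candidate coefficients behave when reader B differs systematically from reader A.

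**Inputs.** The number of participants, 50, is the planned enrolment (SAP 4.2). The documents give no lesion-count distribution, so the following are assumptions, with two sets to show the range:

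- Set 1: 0 lesions in 17 participants, 1 in 13, 2 in 10, 3 in 5, 5 in 3, 8 in 2. The sum is 79 and the sum of squares 301. Mean = 79/50 = 1.58. Variance = 301/50 − 1.58² = 3.5236. 33 participants are positive.
- Set 2: 0 in 18, 1 in 14, 2 in 8, 3 in 5, 4 in 3, 6 in 2. Mean 1.38, and 32 participants are positive.

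**Formulas.** Let m be the mean, s² the variance (divisor n) and c the covariance.

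- Pearson r = c / (sA × sB)
- Lin's CCC = 2c / (sA² + sB² + (mA − mB)²)

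**Set 1, B = 2A.** c = 2 × 3.5236 = 7.0472; sB² = 4 × 3.5236 = 14.0944; mean difference 1.58.
- r = 7.0472 / √(3.5236 × 14.0944) = 1.00
- CCC = 14.0944 / (3.5236 + 14.0944 + 2.4964) = 14.0944 / 20.1144 = 0.70

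**Set 1, two extra lesions in positive participants only.** The covariance of the count with being positive is 1.58 × (1 − 0.66) = 0.5372, and the variance of being positive is 0.66 × 0.34 = 0.2244. So c = 3.5236 + 2 × 0.5372 = 4.598, sB² = 3.5236 + 4 × 0.5372 + 4 × 0.2244 = 6.57, and the mean difference is 2 × 0.66 = 1.32.
- r = 4.598 / √(3.5236 × 6.57) = 0.96
- CCC = 9.196 / (3.5236 + 6.57 + 1.7424) = 9.196 / 11.836 = 0.78

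**Set 1, one extra lesion in positive participants only.** c = 4.0608, sB² = 4.8224, mean difference 0.66.
- r = 4.0608 / √(3.5236 × 4.8224) = 0.99
- CCC = 8.1216 / (3.5236 + 4.8224 + 0.4356) = 8.1216 / 8.7816 = 0.92

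**Both sets together:**

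| Reader B relative to A | Set 1: r / CCC | Set 2: r / CCC |
|---|---|---|
| Twice A | 1.00 / 0.70 | 1.00 / 0.69 |
| A + 2 in everyone | 1.00 / 0.64 | 1.00 / 0.54 |
| A + 2 if positive | 0.96 / 0.78 | 0.95 / 0.72 |
| A + 1 if positive | 0.99 / 0.92 | 0.98 / 0.90 |
| A + random Poisson(1) excess | not run | 0.84 / 0.70 (averages) |

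The value r = 1 for an exact linear shift does not depend on the assumed counts. The CCC values do.

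**If an intraclass correlation was meant, its form matters.** In set 2, the two-way absolute-agreement form gives 0.54 for A + 2 and 0.69 for 2A, almost the same as Lin's coefficient. The consistency form gives 1.00 for A + 2 and 0.80 for 2A, so it shares Pearson's blindness to a constant shift.

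**What the positivity statistics catch.** In set 1, A + 2 in everyone makes B positive in 50/50 against 33/50 for A. Pairwise concordance is 33/50 = 66%. Chance agreement is also 0.66 × 1 + 0.34 × 0 = 0.66, so Cohen's kappa for the pair is 0. Doubling, or adding lesions only in positive participants, leaves participant-level positivity unchanged and concordance at 100%.

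**What Bland-Altman limits would show** (mean difference ± 1.96 SD of the differences, set 1). Doubling: 1.58 (−2.14 to 5.30). Two extra if positive: 1.32 (−0.56 to 3.20). One extra if positive: 0.66 (−0.28 to 1.60).

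**The case against.** A reader might infer that the plan cannot detect a reader who systematically over-counts. The documents do not support that. Bland-Altman plots are planned for the same six count measures and all three reader pairs, and they exist to show systematic difference. SAP 9.12 summarises the number of unequivocal lesions by central reader, and SAP 9.14.3.4 does so per participant. With doubling in set 1, those tables would show means of 1.58 and 3.16. A constant excess in everyone would also pull down the positivity concordance and kappa, as shown above. This objection stands, and it confines the point to the coefficient.

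A reader might also infer that r will be 1 whenever one reader counts more. It is 1 only if the excess is an exact linear function of the other reader's count. Otherwise it is too favourable by a varying amount, sometimes small (0.99 against 0.92).

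Third, the label ICC may mean that an intraclass correlation was intended. That is possible, and the SAP does not settle it. It does not remove the point, because the form would still have to be stated and a consistency form would not serve.

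Finally, the endpoint is exploratory, the protocol asks only for concordance and kappa, SAP 4.1 plans no formal hypothesis testing, and no decision depends on the coefficient. All of this stands and bears on severity.

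**Conclusion.** The point holds in a limited form. The only agreement coefficient named for inter-reader lesion counts is, on its literal wording, a measure of association. It can equal 1 under an exact constant or proportional over-count and is otherwise too favourable. In the positive-only and doubling scenarios it exceeds Lin's coefficient by 0.07 (0.99 − 0.92) to 0.31 (1.00 − 0.69). Those sizes rest on two assumed count distributions and on simple over-count patterns. It is also inconsistent with the coefficient used for counts within a reader.

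The plan does not conceal reader bias, since the plots and by-reader summaries would show it. Participant-level correct detection rate and region-level positive predictive value do not use the coefficient. Severity is minor.

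**What to change.** In SAP 9.14.4.2, replace the Pearson/ICC phrase with one named coefficient, with 95% CI for each reader pair. Either of these would do:

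- Lin's concordance coefficient, which matches 9.14.4.1 and makes the within-reader and between-reader figures comparable; or
- a two-way random-effects, single-reader, absolute-agreement intraclass correlation. The consistency form should be excluded explicitly.

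In the same section, state that the mean difference and limits of agreement from each Bland-Altman plot will be tabulated.

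The cost is a short wording change and a different procedure on the same data, with no extra reads. SAP 1.0 already provides for documenting a change: an SAP amendment if made after signature and before database lock, and a description in the study report for important changes to the analysis.

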## 9.14.5 Disease Management

The impact of the Cu-SAR-bisPSMA PET/CT Day 0 or Day 1 scan will be assessed on change of intended PC treatment via the Disease Management Form completed at screening (Pre-SAR-bisPSMA) and at Day 7 (Post-SAR-bisPSMA). These forms will be completed by the treating physician to document whether any change in planned disease management was warranted due to the Cu-SAR-bisPSMA PET/CT findings.

The proportion of participants with any change in intended PC treatment due to either Day 0, Day 1, both, and sum of participants who had change due to a Cu-SAR-bisPSMA scans will be summarized, with binomial Clopper-Pearson 95% CI.

All disease management data for both timepoints will be listed.

## 9.15 Safety Analyses

All safety analyses will be conducted on the Safety Analysis Set. Where applicable, Participants will be summarized by visit and timepoint.

September 4, 2024 CONFIDENTIAL Page 36 of 46

#### 9.15.1 Adverse Events

AEs will be coded to system organ class and preferred term according to MedDRA, version 25. Pretreatment AEs are defined as AEs that have an onset on or after the date the informed consent was signed but before the time of the first dose of study drug. Treatment-emergent adverse events (TEAEs) are defined as AEs that start or worsen after the first dose of Cu-SAR-bisPSMA.

All AEs with partial or missing dates and times will be considered treatment-emergent unless a partial start date and/or time indicates the AE began before the dose of Cu-SAR-bisPSMA or a stop date indicates the AE ended before the dose of Cu-SAR-bisPSMA.

Summaries will be provided for TEAEs, with the number and percentage of participants reporting each type of event presented. If a participant's reports the same preferred term more than once, it is counted only once within that category. Similarly, if a participant has AEs of two or more preferred terms under the same system organ class, then that patient only counts once for that system organ class. Furthermore, for a given summary, the preferred term will only be counted once at its worst severity and strongest relationship to study drug.

PC symptoms of special interest will be collected and summarized separately by body system.

The following summaries and listings for AEs will be provided:

- An overall summary table of AEs summarizing the number and percent of patients, in the following categories: any AE, any TEAE, TEAEs by highest severity grade, TEAEs by relationship to study drug (related, not related), any serious TEAE, TEAEs leading to discontinuation from the study, TEAEs leading to study drug withdrawal, any TEAEs with a fatal outcome.
- o Incidence of TEAEs by MedDRA system organ class and preferred terms.
- Incidence of TEAEs by MedDRA system organ class, preferred terms, and maximum severity grade.
- o Incidence of related TEAEs by MedDRA system organ class, preferred terms, and maximum severity grade.
- Incidence of TEAEs grade 3 or higher by MedDRA system organ class and preferred term.
- Incidence of related TEAEs grade 3 or higher by MedDRA system organ class and preferred term.
- Incidence of Serious Adverse Events by MedDRA system organ class and preferred term.

September 4, 2024 CONFIDENTIAL Page 37 of 46

- Incidence of related Serious Adverse Events by MedDRA system organ class and preferred term
- o Listing of all AEs (with non-treatment-emergent events flagged).
- o Listing of all AEs for patients who withdrew from study or study drug due to an AE.
- o Listing of all SAEs.

